# 3.2. Study Endpoints

### 3.2.1. Primary Endpoints

### Safety:

The primary safety endpoints are:

- Occurrences, intensity, and relationship to vaccination of immediate Adverse Events (AEs) (30 minutes post-vaccination);
- Occurrences and intensity of solicited local and systemic AEs (for seven days following study vaccine administration);
- Occurrences, intensity, and relationship of unsolicited AEs for 28 days following study vaccine administration;
- Number and percentage of subjects with normal and abnormal, clinically significant urine, haematological and blood biochemistry values, and urinalysis at Days 0, 3, and 28;
- Occurrences of serious adverse events (SAEs), AEs leading to discontinuation, adverse events of special interest (AESIs), medically attended adverse events (MAAEs), new onset of chronic disease (NOCDs), and deaths up to Day 28;
- Occurrences of SAEs, AEs leading to discontinuation, AESIs, MAAEs, NOCDs, and deaths from Day 29 up to Day 182;
- Occurrences of SAEs, AEs leading to discontinuation, AESIs, MAAEs, NOCDs, and deaths from Day 183 up to the end of the study (Day 365).

# **Immunogenicity:**

The primary immunogenicity endpoint is:

HI antibody response induced by adjuvanted and unadjuvanted QVLP and Fluzone HD Quad against the homologous influenza strains on Day 28, compared to Day 0 values. HI antibody titers will be analyzed using the following parameters: geometric mean titers (GMT), seroconversion (SC) rate, seroprotection (SP) rate, and geometric mean fold rise (GMFR).

### 3.2.2. Secondary Endpoints

#### **Immunogenicity:**

The secondary immunogenicity endpoints are:

 MN antibody response induced by adjuvanted and unadjuvanted QVLP and Fluzone HD Quad against the homologous influenza strains on Day 28, compared to Day 0 values. MN antibody titers will be analyzed using the following parameters: GMT, SC rate, and GMFR;

Confidential

Medicago USA Page 13 of 55

- HI antibody response induced by adjuvanted and unadjuvanted QVLP and Fluzone HD Quad against the heterologous influenza strains on Day 28, compared to Day 0 values. HI antibody titers will be analyzed using the following parameters: GMT, SC rate, SP rate, and GMFR;
- HI antibody response (against homologous and heterologous influenza strains) and MN antibody response (against homologous influenza strains) induced by adjuvanted and unadjuvanted QVLP and Fluzone HD Quad on Day 28, compared to Day 0 values, stratified by prior influenza vaccination status, if >25% of the enrolled subjects have received a standard influenza vaccine during the 12 months prior to study vaccination;
- Durability of antibody responses, as determined by HI titers against homologous influenza strains (6 and 12 months post-vaccination compared to Day 0).

### **Safety:**

The secondary safety endpoints are:

- Occurrences, intensity, and relationship to vaccination of immediate AEs (30 minutes post-vaccination), stratified by prior influenza vaccination status, if >25% of the enrolled subjects have received a standard influenza vaccine during the 12 months prior to study vaccination;
- Occurrences and intensity of solicited local and systemic AEs (for seven days following study vaccine administration), stratified by prior influenza vaccination status, if >25% of the enrolled subjects have received a standard influenza vaccine during the 12 months prior to study vaccination;
- Occurrences, intensity, and relationship of unsolicited AEs for 28 days following study vaccine administration, stratified by prior influenza vaccination status, if >25% of the enrolled subjects have received a standard influenza vaccine during the 12 months prior to study vaccination;
- Number and percentage of subjects with normal and abnormal, clinically significant urine, haematological and blood biochemistry values, and urinalysis at Days 0, 3, and 28, stratified by prior influenza vaccination status, if >25% of the enrolled subjects have received a standard influenza vaccine during the 12 months prior to study vaccination;
- Occurrences of SAEs, AEs leading to discontinuation, AESIs, MAAEs, NOCDs, and deaths up to Day 28, stratified by prior influenza vaccination status, if >25% of the enrolled subjects have received a standard influenza vaccine during the 12 months prior to study vaccination;
- Occurrences of SAEs, AEs leading to discontinuation, AESIs, MAAEs, NOCDs, and deaths from Day 29 up to Day 182, stratified by prior influenza vaccination status, if

Medicago USA Page 14 of 55

- >25% of the enrolled subjects have received a standard influenza vaccine during the 12 months prior to study vaccination;
- Occurrences of SAEs, AEs leading to discontinuation, AESIs, MAAEs, NOCDs, and deaths from Day 183 up to the end of the study (Day 365), stratified by prior influenza vaccination status, if >25% of the enrolled subjects have received a standard influenza vaccine during the 12 months prior to study vaccination.

#### 3.3. Treatments

Per protocol version 4.0, subjects will be enrolled into one of the three treatment groups and receive one IM injection of their assigned treatment on Day 0 (refer to Table 1). The volume of injection will be 0.7 mL for all treatments.

The 30  $\mu$ g/strain dose is the full dose of QVLP, used in previous clinical studies. The dosage (30  $\mu$ g/strain) and administration of the active comparator unadjuvanted QVLP is based on data from previous studies as dose used to establish non-inferior efficacy to another approved influenza vaccine in the elderly population and is also the dose most comparable with commonly used licensed vaccines in the elderly. The dosage (60  $\mu$ g/strain) and administration of the active comparator Fluzone HD Quad is in accordance with the approved prescribing information for this vaccine.

# 3.4. Dose Adjustment/Modifications

No dose adjustment/modification is allowed under normal circumstances in this study as the study treatments will be prepared and administered in a single-dose regimen by trained unblinded site staff via IM injection to each subject at each Investigator site on Day 0.

#### 3.5. Stopping Rules

Safety monitoring of safety signals will be performed throughout the study. Refer to protocol version 4.0 section 13.1.12 for more details about safety review. The following events may result in at least a transient halt to the study:

- Any vaccine-related SAE in a subject for which causality cannot be attributed to another cause;
- If 2 or more subjects in a single treatment group experience the same or similar event(s) that cannot be clearly attributed to another cause:
  - o a Grade 3 or higher vaccine-related AE during the study;
  - o a Grade 3 or higher vaccine-related vital sign(s) abnormality;
  - o a Grade 3 or higher vaccine-related clinical laboratory abnormality.

In the case that a pre-defined safety signal is met in any treatment group, subsequent dosing will result in at least a transient halt in the study to permit a complete evaluation of the reported event(s) and to consult an IDMC. A decision as to whether the study can progress

Medicago USA Page 15 of 55

as planned must be made and documented in the event of any safety signal. The analyses will be performed based on the available subject data collected during study period since that even though the IDMC review decides to stop further use of specific dose level, the subjects already administered this dose level of the vaccine will still be followed to the end of the study for all safety and immunogenicity outcomes, if subject permits.

Medicago USA Page 16 of 55

#### 4. General Statistical Considerations

Continuous data (absolute values and change from baseline values) will be described using descriptive statistics (i.e., n, mean, standard deviation (SD), median, minimum, and maximum). Categorical data will be described using frequency count and percentage in each category. For the summary statistics of all numerical variables unless otherwise specified, minimum and maximum will be displayed to the same level of precision as reported. Mean and median will be displayed to one level of precision greater than the data collected. Standard deviation/ standard error will be displayed to two levels of precision greater than the data collected.

For the summary statistics of categorical variables, all percentages will be rounded to one decimal place. Number and percentage values will be presented as xx (xx.x). If the percentage is 100, no decimal is required. If it is below 0.1, it will be reported as "<0.1". P-values will be rounded to three decimal places. If a p-value is less than 0.001 it will be reported as "<0.001." If a p-value is greater than 0.999 it will be reported as ">0.999."

All summary tables will have the population sample size in the column headers in form of N=XXX for each treatment group and all subjects, and the analyses of the immunogenicity and safety endpoints will include comparisons by prior influenza vaccination status, if >25% of the enrolled subjects have received a standard influenza vaccine during the 12 months prior to study vaccination. The five stopped treatment groups (QVLP adjuvanted with AS03 (half dose) 15  $\mu$ g/strain, QVLP adjuvanted with AS03 (half dose) 45  $\mu$ g/strain, QVLP adjuvanted with AS03 (half dose) 30  $\mu$ g/strain and QVLP adjuvanted with AS03 45  $\mu$ g/strain) will also be included in analyses as other treatment groups. All enrolled subject data recorded on CRF and entered into the database will be provided in separate data listings showing individual subject values. Data will be displayed in all listings sorted by treatment group, subject number and visit (time point, if applicable).

All laboratory data will be reported using international system of units (SI).

When count data are presented, the percentage will be suppressed when the count is zero in order to draw attention to the non-zero counts. A row denoted "Missing" will be included in count tabulations where specified on the shells to account for dropouts and missing values. The denominator for all percentages will be the number of subjects in that clinical diagnosis category within the analysis set of interest, unless otherwise specified.

Baseline value is defined as the last non-missing data on or before the IM injection of the study vaccine, unless otherwise specified.

Study Day is the number of days since the administration of the study vaccine, which is counted as Study Day 0. If the assessment date is after the date of the vaccination, the study day is calculated as date of assessment - date of the vaccination + 1. If the assessment date is prior to the date of the vaccination, the study day is calculated as date of assessment - date of the vaccination.

Medicago USA Page 17 of 55

Onset day is calculated as date of event – date of the vaccination +1.

During the programming period, the table/listing/figure shell format and footnote might be edited. And this kind of change is not be considered as analysis changes or impact the analysis results.

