#### 1. Introduction

This statistical analysis plan (SAP) describes the analyses and data presentations for Medicago's protocol CP-PRO-AdjQVLP-020 "A Randomized, Partially-Blinded, Active Comparator-Controlled, Dose-Ranging, Safety, Tolerability, and Immunogenicity Phase 1/2 Study of an Adjuvanted Seasonal Recombinant Quadrivalent VLP Influenza Vaccine in Adults 65 Years of Age and Older" which was issued and finalized as version 4.0 on 08-Mar-2021. The vaccine containing QVLP, which is intended for active immunization for the prevention of influenza disease caused by influenza A subtype viruses and type B viruses, may be able to address several limitations of the currently licensed vaccines. The results of conducted preclinical and clinical studies show that QVLP was well-tolerated and able to induce a substantial antibody response in healthy adult (18 to 64 years) and elderly (65 years of age and older) populations. Given the relatively modest antibody responses elicited by OVLP against some strains and because the HI antibody response is well recognized by Regulatory Agencies to be a correlate of efficacy, Medicago conducts this Phase 1/2 clinical trial to study the possible advantage of administering QVLP with an adjuvant used in licensed vaccine products (AS03) by assessing the safety, tolerability, and immunogenicity of adjuvanted recombinant OVLP in healthy adults 65 years of age and older.

The purpose of the SAP is to ensure the credibility of the study findings by pre-specifying the statistical approaches to the analysis of study data. All statistical analyses detailed in this SAP will be conducted using SAS® 9.4 or higher (SAS Institute Inc., Cary, North Carolina). The SAP will be finalized and signed prior to the clinical database lock (DBL) for the final analysis.

datasets (SDTM & ADaM) including specifications and eCRT packages, development of validated TLFs for the first, second and third interim analyses and the final analysis and, reviewing the statistical part of the Clinical Study Report (CSR). Medicago is responsible for reviewing all aforementioned statistical deliverables. Assignment of subjects to individual PP sets based on PDs will be performed by Medicago (see details in Section 4.4.4).

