# 3. Investigational Plan

# 3.1. Overall Study Design and Plan

This randomized, partially-blinded, active comparator-controlled multi-center, Phase 1/2 study will be conducted at multiple sites to evaluate the safety, tolerability, and immunogenicity of an adjuvanted seasonal recombinant quadrivalent VLP influenza vaccine in adults 65 years of age and older. Overall approximately 120 healthy male and female subjects 65 years of age and older will be enrolled evenly into one of three parallel treatment groups and subjects will be stratified by age into two groups (65 to 74 years of age and 75 years of age and older) and by prior influenza vaccination status (defined as having received a standard influenza vaccine during the 12 months prior to study vaccination). Before protocol version 4.0 became effective:

- In protocol version 2.0, a different randomization was in place with 2 additional treatment groups (QVLP adjuvanted with AS03 (half dose) 15 μg/strain and QVLP adjuvanted with AS03 (half dose) 45 μg/strain) and without prior influenza vaccine status as randomization stratification factor. The enrollment of these two treatment groups was stopped per protocol version 3.0. The number of subjects randomized into these two treatment groups will be documented in the CSR. The six treatment groups included three dose levels of QVLP (15 μg/strain, 30 μg/strain, and 45 μg/strain) with the full dose or QVLP (30 μg/strain) with the half dose of adjuvant AS03, unadjuvanted full dose of QVLP (30 μg/strain), and the active comparator Fluzone HD Quad.
- In protocol version 3.0, there was 3 additional treatments groups (QVLP adjuvanted with AS03 15 μg/strain, QVLP adjuvanted with AS03 (half dose) 30 μg/strain and QVLP adjuvanted with AS03 45 μg/strain). The enrollment of these 3 treatment groups was stopped per protocol version 4.0. The number of subjects randomized into these three treatment groups will be documented in the CSR. Moreover, the planned number of subjects has been decreased 50 to 40 by treatment group.

The three remaining treatment groups include QVLP adjuvanted with AS03 (30 µg/strain), unadjuvanted QVLP (30 µg/strain), and the active comparator Fluzone HD Quad.

**Table 1:** Study Treatment Groups

Treatment Group	Treatments	Dose Level	Planned No. of Subjects
1	QVLP adjuvanted with AS03	30 μg/strain	40
2	QVLP unadjuvanted	30 μg/strain	40
3	Fluzone HD Quad	60 μg/strain	40

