### 4.2. Randomization, Stratification, and Blinding

#### 4.2.1. Randomization and Stratification

The randomization numbers will be allocated to subjects within the appropriate treatment group by the randomization system once all screening procedures, including Day 0 prerandomization procedures, have been completed and the study eligibility is confirmed by the Investigator. Randomization will be stratified by age group (65 to 74 years of age and 75 years of age and older). In addition, after the implementation of the new randomization strategy per protocol version 3.0, prior influenza vaccination status (defined as having received a standard influenza vaccine during the 12 months prior to study vaccination) was also added as a stratification factor (i.e., it was not in place for the randomization of any subjects enrolled prior to protocol version 3.0).

Considering the study design with two scheduled IDMCs, as per protocol version 1.0, the randomization schedule was to include subjects in treatment groups 1-6 and begin the enrolment in treatment groups 7 and 8 once 1st IDMC permits. However, as described previously, two treatment groups (QVLP adjuvanted with AS03 (half dose) 15 ug/strain and QVLP adjuvanted with AS03 (half dose) 45 ug/strain) in protocol version 3.0 and three treatment groups (QVLP adjuvanted with AS03 15 µg/strain, QVLP adjuvanted with AS03 (half dose) 30 µg/strain and QVLP adjuvanted with AS03 45 µg/strain) in protocol version 4.0 were stopped.

The randomization of the two stopped treatment groups in protocol version 3.0 was generated according to the randomization schema (with age group only as stratification factor) planned in the protocol version 1.0 (refer to Appendix 13.2). Some patients enrolled in the 3 treatments groups stopped in protocol version 4.0 were randomized according to the new randomization schema (with age and influenza history vaccine as stratification factor). Patients enrolled after the implementation of protocol version 4.0 will be randomized into the three remaining treatment groups. The randomization schedule will be generated by computer.

Medicago USA Page 18 of 55

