# 13.2. Overview of Randomization Strategy

The description below reflects the randomization strategy before protocol version 3.0.

Note: the five stopped treatment groups (QVLP adjuvanted with AS03 (half dose) 15  $\mu$ g/strain, QVLP adjuvanted with AS03 (half dose) 45  $\mu$ g/strain, QVLP adjuvanted with AS03 15  $\mu$ g/strain, QVLP adjuvanted with AS03 (half dose) 30  $\mu$ g/strain and QVLP adjuvanted with AS03 45  $\mu$ g/strain) were also considered at time of the two IDMC meetings for decision making.

Below list details steps of decision making in chronological order which are to be followed throughout the duration of the study:

- 1. Schedule 1 open: 18 records (3 subjects per treatment groups 1-6)
- 2. Schedule 1 closed
- 3. 1st IDMC
  - If IDMC1 doesn't permit group 7-8 then open schedule 1 (47 subjects per treatment groups 1-6) and study complete
  - If IDMC1 permits group 7-8 then continue as below:
- 4. Schedule 2 open: 6 records (3 subjects per treatment groups 7-8)
- 5. Schedule 2 closed
- 6. Schedule 1 open 282 records (47 subjects per treatment groups 1-6)
- 7. 2nd IDMC
  - If IDMC2 doesn't permit group 7-8 then continuing open schedule 1 (47 subjects per treatment groups 1-6) and study complete
  - If IDMC2 permits group 7-8 then
    - o If group 1-6 is fully enrolled, close Schedule 1 and open Schedule 2 (94 subjects per treatment groups 7-8)> study complete
    - If group 1-6 is not fully enrolled, continuing open schedule 1 till fully enrollment is reached, close Schedule 1 and open Schedule 2 (94 subjects per treatment groups 7-8)> study complete

Numbering of treatment groups in above description is as follows:

QVLP adjuvanted with AS03 15 μg/strain**	1
QVLP adjuvanted with AS03 (half dose) 15 μg/strain*	2
QVLP adjuvanted with AS03 30 μg/strain	3
QVLP adjuvanted with AS03 (half dose) 30 μg/strain**	4
QVLP unadjuvanted 30 μg/strain	5
Fluzone HD Quad 60 µg/strain	6

Medicago USA Page **46** of **55** 

QVLP adjuvanted with AS03 45 μg/strain**	7
QVLP adjuvanted with AS03 (half dose) 45 μg/strain*	8

\*Enrollment into these 2 treatment groups was stopped as per protocol version 3.0.

Medicago USA Page 47 of 55

\*\*Enrollment into these 3 treatment groups was stopped as per protocol version 4.0.

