# 13.3. SAS code for Immunogenicity Analyses

# To calculate adjusted GMT and do the ANOVA:

PROC MIXED data=tab(where=(avisitn = Day <0, 28, 182, 365>)); \*\* to be repeated for each relevant timepoints

BY STRAIN;

CLASS TRT:

MODEL var = TRT; \*\* where var=LOG10(Analysis value)

LSMEANS TRT / DIFF=ALL CL ALPHA=0.05 ADJUST=tukey;

RUN:

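### The tested models pool five stopped arms with the three continuing ones and have no term for enrolment period, so most GMT and GMFR pairs compare arms with different enrolment windows, and the unbiased objective pairs pay for it in the Tukey adjustment

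*SAP*

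**What the plan says.** Group numbers below are those of SAP 13.2.

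- **Inclusion.** SAP 4 states that the five stopped groups "will also be included in analyses as other treatment groups".
- **Models.** SAP 8.1 compares log titres (ANOVA) and log fold rises (ANCOVA with baseline) among treatment groups, with Tukey's test inside the same model. Both models in SAP 13.3 use "LSMEANS TRT / DIFF=ALL CL ALPHA=0.05 ADJUST=tukey". The GMT model contains treatment only; the GMFR model adds log baseline titre. Neither has a term for period, schedule or protocol version, and neither restricts the treatment variable. Seroconversion (SC) and seroprotection (SP) are coded as one Fisher test per strain over all groups.
- **Closures.** For half-dose-adjuvant 15 and 45 µg (groups 2 and 8), SAP 3.1 says: "The enrollment of these two treatment groups was stopped per protocol version 3.0". For full-dose-adjuvant 15 and 45 µg and half-dose-adjuvant 30 µg (groups 1, 7 and 4) it says: "The enrollment of these 3 treatment groups was stopped per protocol version 4.0". Version 4.0 was "issued and finalized as version 4.0 on 08-Mar-2021" (SAP 1).
- **Continuation.** SAP 4.2.1: "Patients enrolled after the implementation of protocol version 4.0 will be randomized into the three remaining treatment groups". These are groups 3, 5 and 6.
- **Late opening.** In SAP 13.2, groups 7 and 8 start on their own list after the first IDMC review: "Schedule 2 open: 6 records (3 subjects per treatment groups 7-8)".
- **Stratification.** Prior influenza vaccination became a stratum only at version 3.0; SAP 4.2.1 says "it was not in place for the randomization of any subjects enrolled prior to protocol version 3.0".
- **Objectives.** SAP 2.1 and 2.2 compare AS03 30 µg (group 3) only with unadjuvanted QVLP (group 5) and Fluzone HD Quad (group 6).

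**The concern.** Randomisation protects a comparison only among subjects who could have been allocated to either arm. When a stopped arm is compared with an arm that kept recruiting, part of the second arm was randomised when the first was no longer available. Any change over time in season, case mix or time since the last influenza vaccine then enters the treatment contrast.

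Eligibility supplies one plausible route. Exclusion criterion 5 bars influenza vaccine in the six months before vaccination. If that criterion held throughout, a person vaccinated in October 2020 could not enter until about April 2021, after version 4.0. The share and recency of prior vaccination could therefore shift with calendar time.

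Two things are at stake. Pairwise p-values for dose and adjuvant contrasts could be read as randomised evidence; protocol 4.2.3 still describes selecting a dose combination, and the protocol synopsis says Tukey's test is there to show pairwise p-values. Separately, the comparisons named in the objectives are judged against a multiplicity family inflated by arms the objectives do not mention.

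**Working it through.** **The plan's own figures.** SAP 4.1 gives 3 × 40 = 120, which reproduces. The eight-group structure in SAP 13.2 also checks: 6 × 3 = 18, 6 × 47 = 282, 2 × 3 = 6 and 2 × 47 = 94, total 400. SAP 4.1 reports no sample size calculation, and the documents give no SD or effect size, so there is no power figure to reproduce. SAP 3.1 leaves the sizes of the stopped arms to the CSR.

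**Enrolment windows** (SAP 3.1, 4.2.1, 13.2):

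| Groups | Opened | Closed |
|---|---|---|
| 3, 5, 6 | Schedule 1 | continued |
| 1, 4 | Schedule 1 | v4.0 |
| 2 | Schedule 1 | v3.0 |
| 7 | Schedule 2, after first IDMC | v4.0 |
| 8 | Schedule 2, after first IDMC | v3.0 |

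**Pairs per strain and parameter.**

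- All pairs: C(8,2) = 28. At Day 28 for homologous HI, 4 strains × 2 parameters × 28 = 224 pairs. With three arms, C(3,2) = 3 and 4 × 2 × 3 = 24.
- Same full window: 3–5, 3–6, 5–6 and 1–4, so 28 − 4 = 24 (86%) do not share one.
- By closing version alone, matched pairs are C(3,2) among 3, 5, 6, plus C(3,2) among 1, 4, 7, plus one for 2–8: 3 + 3 + 1 = 7. So 28 − 7 = 21 (75%) are unmatched.
- Stopped arm against a comparator (5 or 6): 5 × 2 = 10.

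**Possible bias.** Let f be the share of the comparator randomised while the stopped arm was open, and δ the shift in mean log10 titre among the rest. The spurious difference is (1 − f)δ, and the spurious GMT ratio is 10^((1 − f)δ). Both inputs are assumed:

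| f | δ = 0.1 | δ = 0.2 | δ = 0.3 |
|---|---|---|---|
| 0.75 | 1.06 | 1.12 | 1.19 |
| 0.50 | 1.12 | 1.26 | 1.41 |
| 0.25 | 1.19 | 1.41 | 1.68 |

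**Effect on the objective pairs.** The critical |t| is the 95% point of the studentized range divided by √2.

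- Three groups, df = 120 − 3 = 117: 2.374, per-pair two-sided alpha 0.019.
- Eight groups, df 200 assumed: 3.063, per-pair alpha 0.0025. With df 117 or 312 the value is 3.087 or 3.052, so the df assumption matters little.
- An effect with 80% power under three groups is 2.374 + 0.842 = 3.216 standard errors. Under eight groups its power is Φ(3.216 − 3.063) = Φ(0.153) ≈ 0.56, taking the residual SD as the same in both fits (normal approximation).
- With 40 per arm and an assumed SD of 0.5 log10, the standard error is 0.5 × √(2/40) = 0.112. The smallest significant GMT ratio rises from 10^(2.374 × 0.112) = 1.84 to 10^(3.063 × 0.112) = 2.20. For SDs of 0.4 and 0.6 it rises from 1.63 to 1.88 and from 2.08 to 2.58.

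**The case against.** The defence has real substance. The arms in the objectives recruited throughout, so 3 versus 5 and 3 versus 6 carry no non-concurrent-control bias. No objective in SAP 2.1 or 2.2 names a stopped arm. GMFR is baseline-adjusted and SC is defined within subject. Day 0 GMTs are compared by group, so baseline drift would be visible. Immunogenicity analyses are repeated by prior-vaccination status if more than 25% of subjects qualify, which addresses one candidate confounder. Safety is descriptive. All of this stands and limits the point. Post-vaccination GMT and SP remain without baseline adjustment, and baseline adjustment in GMFR may absorb only part of any drift.

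Three stronger readings are tempting, but the documents do not support them.

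- **Most comparisons use non-concurrent controls.** It is true that 25 of 28 pairs contain a stopped arm, but that is not a count of non-concurrent controls. Ten of the 25 are stopped against stopped, groups 1 and 4 share a full window, and only 10 of 28 involve a comparator. Most affected pairs also mix concurrent with non-concurrent subjects.
- **The formulation decision was confounded by late enrollees.** SAP 10 ties that decision to Day 28 HI data in the 12 February 2021 transfer. With the ±2-day window, those subjects were vaccinated by about 17 January (12 February minus 26 days), before version 4.0 of 8 March. No comparator subject enrolled after version 4.0 could be in it. The date of the version 3.0 closure is not given.
- **The bias has a known size.** It does not. Neither the drift nor the concurrent share is in the documents.

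A further objection is that shrinking the Tukey family loosens the objective tests late in the study. SAP 5.0 is dated March 2022, and SAP 4.2.2 lets some sponsor staff see data throughout. That is correct and must be dealt with in the fix.

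**Conclusion.** The point holds in limited form. As written, the SAP tests stopped and continuing arms together without accounting for enrolment period. Of 28 GMT or GMFR pairs, 24 do not share a full window (21 by closing version alone), and 10 set a stopped arm against a comparator that kept enrolling. Those contrasts can mix treatment with calendar time, chiefly for post-vaccination GMT. The omnibus SP test also mixes periods. The 1.06 to 1.68 range is illustrative and rests wholly on assumed drift and concurrency.

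The objective contrasts are not biased. Their cost is stringency: critical |t| of about 3.06 instead of 2.37, and about 56% power where the three-arm family would give 80%. That rests on Tukey's test being run over all eight groups, as SAP 4 and the unfiltered code imply, and on about 40 evaluable subjects per current arm. Correcting this is a cheap improvement; nothing here invalidates the trial.

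**What to change.** In SAP 4, 8.1 and 13.3, fit the GMT and GMFR models, the Tukey comparisons and the SC/SP Fisher tests on the three current arms. Present the stopped arms descriptively, with estimates and 95% CIs.

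If a stopped arm is compared at all, label the comparison exploratory and use only comparator subjects randomised in the calendar period when that arm was open. Matching on schedule will not do, because the original Schedule 2 holds only groups 7 and 8 and has no comparator. If no comparator subject falls in the period, make no comparison.

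Date the change and disclose it in SAP 11, stating that the smaller family makes the objective tests less strict and that some sponsor staff may already have seen unblinded data. Keep the eight-group result as a sensitivity analysis.

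The cost is a filter on treatment, SAP wording, and a randomisation-period variable for any exploratory comparison. The main tables lose formal tests of the closed arms. No new data are needed.
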